There are no prior studies investigating the use of intravenous lidocaine for the management of pain associated with adolescent idiopathic scoliosis surgery. As such, the dosage chosen comes from prior work in abdominal surgery and elective spine surgery^{18,19,22}. These studies have shown lidocaine to be effective in improving pain scores, reducing opioid consumption, and improving patient reported outcomes measures. Lidocaine will be given at the induction of anesthesia until 24 hours after arrival to the Post-Anesthesia Care Unit (PACU) or Pediatric Intensive Care Unit (PICU).

A research pharmacist not involved in the care of the patient will deliver lidocaine, 8mg/mL, in D5W (Baxter International, Deerfield, IL, USA), or D5W (Baxter International) to the operating room for continuous infusion. A separate bag containing 1mg/kg of lidocaine in D5W, or an identical volume of plain D5W, will be delivered for bolus delivery. All solutions will be packaged identically, to avoid accidental unblinding. The study pharmacy will report both loading bolus volume and volume/hr rate for the infusion in the electronic medical record. The total volume of study drug/placebo administered will be recorded.

E Study Design

E1 Overview or Design Summary

Anesthesia, other than the lidocaine, will be given as standard of care per physician discretion

Study Drug: After a 1 mg/kg lidocaine bolus with induction, a lidocaine 1 mg/kg (IBW)/hr IV infusion with maximum dose of 200 mg/hr or D5W (placebo) at equal volume rate of administration will begin prior to skin incision and continue intraoperatively for duration of the case. Study drug will be discontinued upon 24 hours of stay in PICU or PACU postoperatively. Study drug will be dosed according to ideal body weight (IBW). Patient height, weight, age, and gender will be delivered to the study pharmacy prior to the day of surgery for calculation of IBW and dosing parameters.

E2 Subject Selection and Withdrawal

Study participants will be AIS patients recruited from Orthopaedic Spine clinics at Center of Advance Medicine Barnes Jewish and St. Louis Children's hospitals. Given the single disease investigated, AIS, we anticipate that our results will be generalizable to AIS patients at other institutions. We will enroll 50 patients, 25 per group, over two years. Approximately 60 AIS surgeries are performed per year at our institution.

2.a Inclusion Criteria

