1. Adolescent idiopathic scoliosis indicated for posterior spinal fusion.
2. Ages between 12 and <18 years of age.
3. Parent/Guardian capable of providing informed consent for study participation.

2.a Exclusion Criteria

1. Age < 12 or > 17.9 years old.

Intravenous Lidocaine to Reduce Postoperative Opioid Consumption and Improve Recovery After Posterior Spinal Fusion for Adolescent Idiopathic Scoliosis

- 2. Unable to obtain consent for the surgical intervention or study, or if mental capacity prohibits the ability to provide consent and complete patient-reported outcomes tools.
- 3. Diagnosis of sepsis or infection
- 4. Diagnosis of primary or metastatic malignancy.
- 5. Participation in another clinical trial.
- 6. Past or current diagnoses of a cardiac arrhythmia or first/second degree heart block.
- 7. Past or current seizure disorders.
- 8. Known allergy to bupivacaine.
- 9. Significant liver disease
- 10. Significant kidney disease
- 11. Known pregnancy
- 12. Known allergy to lidocaine and/or benzocaine
- 13. Planned anterior approaches for treatment of scoliosis deformity.
- 14. Limited English proficiency (e.g. unable to obtain informed consent for surgery without a translator)
- 15. Ward of the State children

2.b Subject Recruitment Plans and Consent Process

Description of Recruitment Process

- 1. Subject selection will be equitable. No patient will be included or excluded on the basis of gender, race, religion, national origin, or sexual orientation. Refusal to participate in the study will not affect the patient's access to care or surgical priority.
- 2. The research coordinator will identify all patients with AIS in the orthopedic clinics. An interview will determine study eligibility.
- 3. Subjects will not be compensated for their participation. There will be no advertisement material. All follow-up care is according to standard of care, with no non-standard tests, imaging, or follow-up appointments.

2.c Randomization Method and Blinding

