The low plasma levels have not been associated with hemodynamic instability nor have they been associated with changes in cardiac contractility. No interactions with the autonomic nervous system have been reported and there are no known effects on sinoatrial conduction. Lidocaine is metabolized by the liver, with less than 10% excreted in urine. Complications are rare. Despite concerns for arrhythmias, intravenous lidocaine has been used in cardiothoracic surgery without increased rates of cardiac complications. Given this volume of evidence, we feel that intravenous lidocaine in the setting of AIS surgery is safe.

3.b Treatment Regimen

After a 1mg/kg IBW lidocaine bolus with induction, a lidocaine 1 mg/kg/hr (IBW) IV infusion with maximum dose of 200 mg/hr or D5W (placebo) at equal volume rate of administration will begin prior to skin incision and continue intraoperatively for duration of the case. Study drug will be discontinued upon 24 hours of stay in either PACU or PICU postoperatively.

Method for Assigning Subjects to Treatment Groups

Patients consenting to randomization will be randomized 1:1 to the control vs study groups. A permuted randomized block approach¹ with blocks of size 4, 6 and 8. Given the relatively large number of patients to be enrolled, no stratification will be performed. After 30 patients are enrolled, an interim analysis, without unblinding, of baseline covariates will be performed to ensure equal distribution between groups. If distribution is uneven for covariates concerning for confounding, then stratification by these covariates will be employed to ensure equal distribution with randomization.

3.c Blinding of Study Drug

This is a Phase IV, randomized, triple-blind, placebo-controlled trial with two study groups: postoperative standard of care with opioid patient controlled analgesia (PCA) and IV lidocaine infusion versus postoperative standard of care plus normal saline placebo. Block randomization into one of the two groups will be based on a random table generated using an R-program. Group 1 (Study) will receive intravenous lidocaine during and after posterior spinal fusion for AIS. Group 2 (Control) will receive saline placebo during and after surgery.

F Study Procedures

F1 Screening for Eligibility

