The research coordinator will screen all new patients for enrollment qualifications according to inclusion and exclusion criteria. Eligible patients will be approached by the study coordinator to introduce the study and obtain consent prior to surgery.

We will screen that the following tests to confirm study eligibility:

1. Negative result of pregnancy test by urine hCG
2. Normal CMP tests to assess liver and kidney function

F2 Schedule of Measurements

The research coordinator will screen all new patients with Adolescnet Idiopathic Scoliosis (AIS) for enrollment qualifications according to inclusion and exclusion criteria. Eligible patients will be approached by the study coordinator to introduce the study and obtain consent prior to surgery.

Patients consenting to randomization will be randomized 1:1 to the standard of care or study intervention arms. A permuted randomized block approach¹ with blocks of size 4, 6 and 8. Group 1 (Study) will receive intravenous lidocaine during and after posterior spinal fusion for AIS. Group 2 (Control) will receive saline placebo during and after surgery.

After a 1mg/kg lidocaine bolus with induction, a lidocaine 1 mg/kg (IBW)/hr IV infusion with maximum dose of 200 mg/hr or D5W (placebo) at equal volume rate of administration will begin prior to skin incision and continue intraoperatively for duration of the case. Study drug will be discontinued upon 24 hours of stay in either PACU or PICU postoperatively.

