The anticipated outcome is decreased in-hospital opioid consumption for those patients treated with intravenous lidocaine. Other anticipated outcomes are improved recovery as measured by PROMIS-M and PROMIS-PI measures at 6 weeks, 3 months, 6 months, and 12 months after surgery. We anticipate that the anti-inflammatory effect of lidocaine will reflect a smaller postoperative inflammatory response as measured by IL-10, IL-4, and IL-12.

F3 Safety and Adverse Events

Serum lidocaine levels will be drawn at 12 hours after incision and reviewed by an individual independent from the study team. Lidocaine toxicity will result in immediate cessation of study drug, unblinding, and reporting to the Medical Monitor and IRB. If intraoperative surgical, medical, or anesthetic complications occur, including cardiac arrhythmia, the study medication will be stopped and the patient withdrawn from the study. The patient will be analyzed in an intent-to-treat analysis, though they will be excluded from as-treated analyses. After surgery, patients will be seen and examined twice daily with attention to postoperative complications. As the study-drug will have completed infusion, all complications will be recorded though patients will remain enrolled in the study and analyzed per-protocol. All adverse events will be recorded up to 12 weeks after surgery. These will be captured via interview at the visit or via telephone if a clinic visit is not possible. Readmission for any reason will be recorded and details of this hospitalization will be recorded. Any reason reasonably related to the research protocol will be reported to the Medical Monitor and the IRB.

We believe there are minimal risks associated with participation in this clinical trial and with the study intervention (intravenous lidocaine). The most concerning serious adverse event that might be attributed to systemic lidocaine administration is cardiac arrhythmia/arrest. Therapeutic serum concentrations are far lower than toxic levels and we believe the risk of serious adverse events to be low. The intervention will not add time to the surgical intervention and, thus, does not pose additional risk from this perspective. All patients will receive standard of care treatment before, during, and after surgery and the study intervention will pose no risk to this.

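### F3 and I1 treat the infusion as finished once surgery ends, but study drug runs for another 24 hours, so a postoperative arrhythmia not classed as lidocaine toxicity has no explicit stop-drug instruction

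*Combined protocol and SAP*

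**What the plan says.** Four sections of the combined protocol and SAP set the end of study drug, and they agree.

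- D2 (Dose Rationale): "Lidocaine will be given at the induction of anesthesia until 24 hours after arrival to the Post-Anesthesia Care Unit (PACU" or the PICU.
- E1 (Overview): "Study drug will be discontinued upon 24 hours of stay in PICU or PACU postoperatively".
- 3.b (Treatment Regimen) and F2 (Schedule of Measurements): "Study drug will be discontinued upon 24 hours of stay in either PACU or PICU postoperatively".

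F2 and 3.c also describe the active arm as treated on both sides of the end of the operation: "Group 1 (Study) will receive intravenous lidocaine during and after posterior spinal fusion for AIS".

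F3 (Safety and Adverse Events) and I1 (Study Monitoring Plan) then turn to complications found after surgery. Both use the same sentence: "As the study-drug will have completed infusion, all complications will be recorded though patients will remain enrolled in the study and analyzed per-protocol". In both sections it follows a rule that stops study medication and withdraws the patient for complications during the operation, arrhythmia included.

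F3 has two further rules for the individual patient. Lidocaine toxicity leads to immediate cessation, unblinding and reporting. A later paragraph says that if a problem such as cardiac arrest or seizure arises once study medication has been given, the patient is unblinded and followed.

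**The concern.** The sentence in F3 and I1 gives a reason for its rule: complications need only be recorded because no drug is running. For the first 24 hours after arrival in PACU or PICU, the dosing sections say that drug is running. The rule therefore rests on a false premise during that period.

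This matters most for cardiac arrhythmia. F3 singles it out, with arrest, as the drug-related event of greatest concern. In the operating room an arrhythmia stops the drug without anyone having to decide whether lidocaine caused it. Hours later, on the same infusion, the only general rule for complications assumes there is nothing to stop. The participants are minors aged 12 to under 18, and the treating staff are blinded.

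**Working it through.** No sample size, power or error rate bears on this point, so the check sets the texts side by side.

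**1. Timeline.** Take arrival in PACU or PICU as hour 0. Under D2, E1, 3.b and F2, study drug is planned from hour 0 to hour 24. At any hour t before 24, 24 − t planned hours remain. No section gives a shorter infusion. F3 and I1 state no duration; they only assert that the infusion is over. From hour 0 to hour 24 that assertion and the dosing sections cannot both be right. After hour 24 the assertion is correct.

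**2. Which patient-level rule applies when.**

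| Rule | Where | During the operation | Hours 0 to 24, drug running | After hour 24 |
|---|---|---|---|---|
| Complication, including arrhythmia: stop drug, withdraw patient | F3, I1 | Applies | Does not apply (intraoperative only) | No drug to stop |
| Lidocaine toxicity: stop, unblind, report | F3 | Applies | Applies if the event is classed as toxicity (undefined) | No drug to stop |
| Problem arising after study drug was given: unblind, follow | F3, later paragraph | Applies | Arguable; orders no cessation | Arguable |
| Record, keep enrolled | F3, I1 | Does not apply | Applies by its timing, though its reason is false | Applies, and its reason is true |

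**3. Rules above patient level.** For a serious event the Medical Monitor looks for the root cause, informs the principal investigator if study drug may be responsible, and may recommend stopping the study. I1 provides a blinded review after 15 patients, unblinding if events look imbalanced, and early termination if serious events are linked to treatment. None of these tells staff whether to stop one patient's infusion.

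**4. An arrhythmia between hours 0 and 24.** The intraoperative rule does not reach it. The toxicity rule reaches it only after a judgement for which the protocol gives no criteria. The unblinding sentence, read broadly, reveals the allocation and no more. By its timing the record-only rule applies. No line says to stop the drug.

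**5. Does the toxicity rule operate in this window?** Yes. Let s be the hours from incision to arrival, with s at least 0. The infusion ends s + 24 hours after incision, and F3 draws the serum level at 12 hours. Planned infusion remaining at the draw is (s + 24) − 12 = s + 12, so at least 12 hours. Toxicity found at that draw can therefore still stop a running infusion. This limits the gap to events not classed as toxicity.

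**6. The reading that would remove the contradiction.** Suppose the phrase about the period after surgery means after the 24-hour infusion. The premise then becomes true, but hours 0 to 24 have no general complication rule. The missing stop instruction remains.

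**The case against.** The strongest reply is that little is left uncovered. The toxicity rule has no time limit and does not require a serum level as proof. Since F3 itself links arrhythmia to lidocaine, a clinician who suspects the drug already has grounds to stop. The unblinding sentence can be read to include postoperative arrest or seizure. Adverse events go at once to the principal investigator, patients are in PACU or PICU under standard care, and those with "Past or current diagnoses of a cardiac arrhythmia or first/second degree heart block" are excluded at entry. The disputed sentence is also mainly about enrolment and analysis status, not drug management.

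Most of this stands, and it narrows the point. It does not close the gap. Suspicion of toxicity is a judgement that the intraoperative rule does not ask for. The unblinding sentence refers back to intraoperative problems and, even read broadly, orders no cessation. The exclusions act before treatment starts. Whatever its main purpose, the sentence tells staff that the infusion has ended when it has not.

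A reader might infer that the protocol orders staff to continue lidocaine through an arrhythmia. It does not: it is silent on stopping, and clinical judgement remains available.

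A reader might also infer that F3 contradicts itself, because patients are examined twice daily after surgery. Such examinations are compatible with a finished infusion, and F3 states no infusion length. The conflict appears only when F3 and I1 are read against D2, E1, 3.b and F2.

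**Conclusion.** The point holds as a contradiction between current sections, with a limited safety consequence. In F3 and I1 a record-only rule rests on a premise that four dosing sections make false for 24 planned hours per patient. During those hours a cardiac arrhythmia not classed as lidocaine toxicity has no explicit stop instruction, although the same event stops the drug in the operating room.

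The conclusion assumes only that the infusion runs as D2, E1, 3.b and F2 state. It does not depend on operating time.

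The consequence cannot be counted in patients, because the documents give no complication rate. A reader might multiply 25 lidocaine patients by 24 hours to get 600 patient-hours and treat that as the size of the problem. That figure restates the planned regimen: it measures exposure, not risk, and adds nothing to severity. The case for correction rests on the kind of event, the age of the participants and the ease of the remedy.

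A reader might also infer a bias in the trial's results from the closing words of the sentence. The documents do not support that. The intent-to-treat analysis is unaffected, and the per-protocol and as-treated sets are not defined well enough to trace any effect.

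**What to change.** In both F3 and I1:

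- Delete the statement that the infusion is already complete, and limit the record-only rule to events after the infusion has ended.
- Keep the intraoperative stop-and-withdraw rule exactly as it is. It covers any complication during the operation without a test of relatedness, and the new text must not narrow it.
- Add a rule for the postoperative infusion: study drug is stopped for cardiac arrhythmia or arrest, seizure, suspected lidocaine toxicity, or any complication that the treating clinician or Medical Monitor considers possibly related to study drug. Patients stopped under this rule stay in safety follow-up and in the intent-to-treat analysis.

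In the later paragraph of F3, align the unblinding sentence with this rule so that it also orders cessation if drug is running. No change to the analysis sets is needed for this point.

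The cost is rewording at two places in F3 and one in I1, with the investigator and Medical Monitor agreeing the stop criteria. It needs no extra patients, visits or procedures. The one downside is that a few patients may receive a shorter infusion, which could slightly dilute the treatment effect in a trial of 50.

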Both the leukocyte frequencies and leukocyte cell surface phenotype will be measured by flow cytometry. This approach will allow hypothesis-based assessment of pathways demonstrated to contribute to the postoperative immune phenotype, while also providing data for a discovery-driven analysis to define novel mechanisms. Patients will be identified based on inclusion/exclusion criteria as described above. Blood samples with following time points: immediately preoperatively, 4 hours and 8 hours post incision, day 1 post surgery, and day 2-3 post surgery. All blood samples will be collected into 6 ml EDTA-containing vacutainers and three aliquots prepared for fixation by mixing 1.25 ml blood with 1.75 ml Proteomic Stabilizer (Smart Tube, Inc, San Carlos, CA). Following fixation, samples will be stored at -80 °C until flow cytometric analysis. For each patient and time point, one aliquot of the fixed and frozen blood will be used for immunophenotyping. The remaining aliquots will be used for mass cytometry as described and preserved as a "biobank" for potential future studies.

We will analyze signaling events in all major leukocyte subsets and compare phospho-signal median intensities between the different time points and treatment groups to define any immune modulatory effects of lidocaine during surgery.

The primary outcome measure is total, in-hospital opioid consumption following surgery for AIS. Opioid consumption will be measured in morphine-equivalent dosage (MED), to allow for the use of different opioid medications (e.g. fentanyl, hydromorphone, oxycodone) over the course of care.

Secondary outcome measures to assess recovery are the Patient Reported Outcomes Measurement Information System (PROMIS) Mobility (M) and Pain Interference (PI) domains. PROMIS is a general measure of health administered over particular health domains. The SRS-22 will be used in assessing the quality of life in AIS patients. The SRS-22r includes 22 items distributed among five different factors (pain, self-

Intravenous Lidocaine to Reduce Postoperative Opioid Consumption and Improve Recovery After Posterior Spinal Fusion for Adolescent Idiopathic Scoliosis

image/appearance, function/activity, mental health, and satisfaction with management). Each component includes five items, except for the “satisfaction with management”, which only contains two items. Secondary measures to assess the anti-inflammatory effect of lidocaine will be serum levels of IL-10, IL-4 and IL-12.

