Safety measures to minimize/eliminate risks to human subjects and study personnel include the use of the Medical Monitor and immediate reporting of any adverse (expected or unexpected) to the project PI and project manager. If any intraoperative complications occur, such as but not limited to cardiac arrest or seizure, the study medication will not be administered and the patient will be excluded from the study. However, if one of these problems occurs after the application of the study medication the patient will be unblinded. The patient will be followed for the occurrence of further adverse events or complications.

For any serious adverse event, the Medical Monitor at the enrollment site will perform a root cause analysis and will notify the project PI in the study medication is believed to be a potential cause of the adverse event. The Monitor may recommend stopping the study. Any serious adverse event will be reported to the PI and the IRB within 10 working days.

F4 Study Outcome Measurements and Ascertainment

The primary outcome measure is total, in-hospital opioid consumption following surgery for thoracolumbar trauma. Opioid consumption will be measured in morphine-equivalent dosage (MED), to allow for the use of different opioid medications (e.g. fentanyl, hydromorphone, oxycodone) over the course of care.

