After the first 15 patients are enrolled, a group consisting of the Principal Investigator and an unengaged physician will review the AE/SAE data. The data will be reviewed blinded. If intraoperative surgical, medical, or anesthetic complications occur, including cardiac arrhythmia, the study medication will be stopped and the patient withdrawn from the study. The patient will be analyzed in an intent-to-treat analysis, though they will be excluded from as-treated analyses. After surgery, patients will be seen and examined twice daily with attention to postoperative complications. As the study-drug will have completed infusion, all complications will be recorded though patients will remain enrolled in the study and analyzed per-protocol.

Special attention will be given if adverse events occur in a higher frequency than expected given patient age and health condition. Serious adverse events, or those that are life threatening, result in death, prolonged hospitalization, readmission, cause persistent disability or require urgent intervention to prevent permanent morbidity will be monitored for up to 30 days after the drug is administered. If there appears to be an imbalance in AE/SAE, unblinding and analysis will ensue to determine if the study should continue. Early termination will occur if SAEs are linked to the treatment arm.

After 10 patients have completed the hospital phase of the study, flow and mass cytometry will be performed to ensure we are capturing cell types and signaling proteins as anticipated.

All protocol violations and SAE's will be reported to HRPO within the WU HRPO policies and procedures reporting guidelines
SAEs will be tracked through resolution.

J References

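### F3 requires unblinding after any intraoperative complication once study drug has been applied; F3's other rule and I1 are silent on it, and no section limits who learns the arm before the primary outcome accrues

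*Combined protocol and SAP*

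**What the plan says.** Section 3.c (Blinding of Study Drug) sets the standard: "This is a Phase IV, randomized, triple-blind, placebo-controlled trial with two study groups".

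F3 (Safety and Adverse Events) then deals with intraoperative complications in two places.

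- **First paragraph.** "If intraoperative surgical, medical, or anesthetic complications occur, including cardiac arrhythmia, the study medication will be stopped and the patient withdrawn from the study". The analysis status follows: "The patient will be analyzed in an intent-to-treat analysis, though they will be excluded from as-treated analyses". Unblinding is not mentioned. The sentence just before does name it, for a different trigger: "Lidocaine toxicity will result in immediate cessation of study drug, unblinding, and reporting to the Medical Monitor and IRB".
- **Third paragraph.** "If any intraoperative complications occur, such as but not limited to cardiac arrest or seizure, the study medication will not be administered", and the patient is excluded. The next sentence reads: "However, if one of these problems occurs after the application of the study medication the patient will be unblinded".

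I1 (Study Monitoring Plan) repeats the stop, withdraw and intent-to-treat wording of F3's first paragraph, again without mentioning unblinding for these events. I1 has a separate unblinding trigger, an apparent imbalance in adverse events between arms.

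On timing, section 3.b (Treatment Regimen) starts the drug at the beginning of anaesthesia ("After a 1mg/kg IBW lidocaine bolus with induction"), with the infusion under way before incision. F2 defines the endpoint: "The primary outcome measure is total, in-hospital opioid consumption following surgery for AIS". Section 3.c describes postoperative care with opioid patient-controlled analgesia (PCA).

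**The concern.** The rule in F3's third paragraph is mandatory and its list of events is open. It does not ask whether the complication could be due to lidocaine, whether it was serious, or whether knowing the arm would help the patient. Read literally, a purely surgical complication breaks the blind.

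The primary outcome is sensitive to this. Opioid use depends on what staff give and on what the patient self-administers. It is counted after surgery, and so after an intraoperative unblinding. The affected patients stay in the intent-to-treat analysis. If those who treat them, those who record their opioid use, or the patients themselves learn the arm, expectation can influence the amount given or recorded.

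Two further matters depend on the same gap. First, a clinician following F3's first paragraph or I1 would find no instruction to unblind, while one following F3's third paragraph would find a requirement, so the same event could be handled differently. Second, I1 says the adverse-event review after 15 patients is done blinded by a group that includes the principal investigator. That may not hold if the investigator has been told the arm of the patients whose events are under review.

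**Working it through.** **1. Do the passages cover the same event?** Yes. F3's first paragraph and I1 cover surgical, medical or anaesthetic complications during the operation, arrhythmia included. F3's third paragraph covers any intraoperative complication, with cardiac arrest and seizure only as examples.

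**2. Do they conflict?** All the instructions can be followed together: stop the drug, withdraw the patient, keep the patient in the intent-to-treat analysis, unblind. The first paragraph and I1 do not say that the blind is kept. The omission still matters, because F3's first paragraph pairs stopping with unblinding for lidocaine toxicity and then leaves unblinding out of the next sentence. The passages are inconsistent without being strictly contradictory.

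**3. Which events fall after application of study drug?** The preceding sentence in F3 deals with drug not yet given, so the natural meaning is after the drug has started. Reading it as after the drug has finished would empty the sentence: section 3.b runs the infusion until 24 hours of PACU or PICU stay, so no intraoperative event could qualify. With the bolus at induction, nearly every intraoperative complication is caught.

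**4. Who is told?** No section says. Hence the consequence for opioid use is that it may be affected, not that it will be.

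**5. The plan's own figures (G1).** Inputs: d = 0.8, SD 37 mg, mean 149 mg, two-sided 0.05, 80% power, 25 per group.
- Target difference: 0.8 × 37 = 29.6 mg, and 29.6 / 149 = 19.9%, matching the stated reduction of about 20%.
- Sample size, normal approximation: 2 × (1.960 + 0.842)² / 0.8² = 24.5, so 25 per group. This reproduces the plan (an exact t-test gives 25.5, so 26).

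**6. How many patients?** The documents give no complication rate, so p is an assumption. Expected number = 50p; chance of at least one = 1 − (1 − p)^50.

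| Assumed rate p | Expected unblinded of 50 | Chance of at least one |
|---|---|---|
| 1% | 0.5 | 39% |
| 2% | 1 | 64% |
| 5% | 2.5 | 92% |
| 10% | 5 | 99% |

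**7. How much bias?** Each patient is 1/25 = 4% of an arm. Suppose k patients per arm are unblinded and their opioid use shifts by a fraction s of 149 mg, down in one arm and up in the other. The shift size and its direction are both assumptions. Bias in the mean difference: b = 2 × s × 149 × k / 25.
- k = 1: s = 0.1 gives 1.2 mg; s = 0.3 gives 3.6 mg.
- k = 3: s = 0.1 gives 3.6 mg; s = 0.3 gives 10.7 mg. Six patients of 50 is 12%, just above the assumed range of rates.
- Putting k = 25p gives b = 2 × s × 149 × p: 0.3 to 0.9 mg at p = 1%, and 3.0 to 8.9 mg at p = 10%.

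**8. Effect on the test.** The standard error of the difference is 37 × √(2/25) = 10.5 mg. With no true effect, the chance of a significant result is Φ(b/SE − 1.96) + Φ(−b/SE − 1.96). This is 5.1% to 6.3% for k = 1 and 6.3% to 17.6% for k = 3, against a nominal 5%.

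**The case against.** The strongest defence is that F3's first paragraph and I1 are silent on unblinding and do not forbid it. That stands. A reader might infer that those passages keep the blind, or that under them only patients with lidocaine toxicity would be unblinded. The documents support neither reading: no sentence preserves the blind after a complication, I1 never mentions toxicity, and I1 has its own trigger in an adverse-event imbalance.

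A reader might also infer that patients and ward staff will know the arm and that the primary result will therefore be biased. The documents do not say that anyone on the ward, the patient, or those recording opioid use is told. That objection also stands.

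The as-treated analyses exclude these patients, so a planned comparison without them exists. This helps only in part. It leaves the intent-to-treat result unprotected, and these patients also had their drug stopped, so a difference between the two analyses could not be attributed to unblinding.

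Finally, F3 presents unblinding as a safety measure in a trial of minors, and the size rests wholly on assumptions. Both points are fair. The first is why the triggers belong to the sponsor and the Medical Monitor. The second is why the size is given as a range starting at 1%. What survives is that F3 contains a mandatory, open-ended unblinding rule, and that no section limits who learns the arm.

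**Conclusion.** The concern holds in a limited form. Followed as written, F3's third paragraph breaks a triple blind for nearly every patient with an intraoperative complication, before the primary outcome accrues, and these patients remain in the intent-to-treat analysis. F3's first paragraph and I1 address the same events without mentioning unblinding, and the three passages need to be reconciled.

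The likely size is modest. At assumed complication rates of 1% to 10%, 0.5 to 5 of 50 patients are affected. With an assumed opposite shift of 10% to 30% of the mean, one patient per arm moves the estimate by 1.2 to 3.6 mg, which is 4% to 12% of the 29.6 mg target (1.2/29.6 and 3.6/29.6). The effect grows if complications are common, and it could be nil if disclosure is in practice confined to people with no part in opioid dosing or recording. The documents settle neither question. The wording should be corrected, but this is not evidence that the primary result is invalid.

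**What to change.** Reconcile the first and third paragraphs of F3 with I1 into a single code-break rule that both sections cite. The sponsor and Medical Monitor should set the safety triggers; this review proposes none, and does not address when study drug is stopped. The rule should state that:

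- when the blind is broken, the study pharmacy discloses the arm only to those who need it for that patient's care or for safety reporting;
- staff who record opioid use, the investigators and, where possible, the patient stay blinded;
- each code break is logged with its time and reason.

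Add to G2, which makes no provision for unblinded patients, a sensitivity analysis of the primary outcome that flags them. Report the number unblinded in each arm beside it. If the analysis leaves these patients out, it should be read with caution, because a complication after randomization may itself be related to treatment.

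The cost is protocol wording in F3, I1 and G2 and a little added procedure and logging. Unblinding remains available whenever safety needs it.
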